7.6.2 Serious Adverse Events

Serious adverse events will be summarized by treatment group. These analyses will be performed on the All Treated LAG-3 Positive Subjects, All Treated LAG-3 Negative Subjects, and All Treated Subjects.

- Overall summary of SAEs by worst CTC grade (any grade, grade 3-4, grade 5) presented by SOC/PT
- Overall summary of drug-related SAEs by worst CTC grade (any grade, grade 3-4, grade 5) presented by SOC/PT

All analyses will be conducted using the 30-day safety window.

A by-subject SAE listing will be provided for the “enrolled subjects” population.

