9.2.1 Time Period and Frequency for Collecting AE and SAE Information

The collection of nonserious AE information should begin at initiation of study treatment until the time points specified in the Schedule of Activities (Section 2). Nonserious AE information should also be collected from the start of a placebo lead-in period or other observational period intended to establish a baseline status for the participants.

Sections 5.6.1 and 5.6.2 in the Investigator Brochures (IBs) represent the Reference Safety Information to determine expectedness of serious adverse events for expedited reporting.

All SAEs must be collected from the time of signing the consent, including those thought to be associated with protocol-specified procedures and within 100 days of discontinuation of dosing.

For participants randomized/assigned to treatment and never treated with study drug, SAEs should be collected for 30 days from the date of randomization.

The investigator must report any SAE that occurs after these time periods and that is believed to be related to study drug or protocol-specified procedure, (e.g. a follow-up skin biopsy).

All nonserious AEs must be collected at the start of study treatment until the time points specified in the Schedule of Activities (Section 2).

- Medical occurrences that begin before the start of study treatment but after obtaining informed consent will be recorded on the appropriate section of the eCRF module.
- All SAEs will be recorded and reported to Sponsor or designee within 24 hours, as indicated in Appendix 3.
- The investigator will submit any updated SAE data to the sponsor or designee within 24 hours of updated information being available.

Investigators are not obligated to actively seek AEs or SAEs in former study participants. However, if the investigator learns of any SAE, including a death, at any time after a participant has been discharged from the study, and he/she considers the event reasonably related to the study treatment or study participation, the investigator must promptly notify the sponsor.

The method of evaluating, and assessing causality of AEs and SAEs and the procedures for completing and reporting/transmitting SAE reports are provided in Appendix 3.

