9.2.2 Method of Detecting AEs and SAEs

Adverse events can be spontaneously reported or elicited during open-ended questioning, examination, or evaluation of a participant. Care should be taken not to introduce bias when

collecting AE and/or SAEs. Inquiry about specific AEs should be guided by clinical judgement in the context of known adverse events, when appropriate for the program or protocol.

All nonserious AEs (not only those deemed to be treatment-related) should be collected continuously during the treatment period and for a minimum of 100 days following discontinuation of study treatment.

Every AE must be assessed by the investigator with regard to whether it is considered immune-mediated. For events which are potentially immune-mediated, additional information will be collected on the participant's case report form.

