10.3.3 Safety Analyses

All safety analyses will be performed on the Safety Sample.

Endpoint	Statistical Analysis Methods

Secondary
 
The Safety and tolerability objective will be measured by the incidence of adverse events (AEs), serious adverse events (SAEs), adverse events leading to discontinuation, deaths, and laboratory abnormalities in each arm by LAG-3 group and overall	
Safety analyses will be performed in all treated participants. Descriptive statistics of safety will be presented using National Cancer Institute (NCI) Common Terminology Criteria for Adverse Events (CTCAE) version 5.0 by treatment group. All on-study AEs, treatment-related AEs, SAEs, and treatment-related SAEs will be tabulated using worst grade per NCI CTCAE v 5.0 criteria by system organ class and preferred term. On-study lab parameters including hematology, chemistry, liver function, and renal function will be summarized using worst grade NCI CTCAE v 5.0 criteria.

[figure not shown]

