3 OBJECTIVES

Table 3-1: Objectives and Endpoints

Objectives	Endpoints
Primary Objective:	
To compare ORR of BMS-986213 in combination with chemotherapy, with ORR of nivolumab in combination with chemotherapy, by BICR, in randomized subjects with untreated, unresectable, and either locally advanced, or metastatic LAG-3 positive GC or GEJ adenocarcinoma.	ORR in subjects who are LAG-3 positive. ORR is defined as the number of subjects with a BOR of CR or PR divided by the number of randomized subjects in each arm. BOR is defined as the best response designation as determined by the BICR, recorded between the date of randomization and the date of objectively documented progression (per Response Evaluation Criteria in Solid Tumors [RECIST 1.1]), death due to any cause, or the date of subsequent anticancer therapy, whichever occurs first.
Secondary Objectives:	
To assess the overall safety and tolerability of BMS-986213 in combination with chemotherapy vs. nivolumab in combination with chemotherapy in treated subjects with advanced or metastatic GC or GEJ cancer.	The incidence of AEs, SAEs, AE leading to discontinuation, deaths, and laboratory abnormalities in each arm.
To compare ORR of BMS-986213 in combination with chemotherapy, with ORR of nivolumab in combination with chemotherapy, as assessed by investigator, in randomized subjects with untreated, unresectable, and either locally advanced, or metastatic LAG-3 positive GC or GEJ adenocarcinoma.	ORR is defined as above, as the number of subjects with a BOR of CR or PR as assessed by the investigator using RECIST 1.1, divided by the number of randomized subjects in each Treatment Arm.
To compare ORR by BICR and by investigator of BMS-986213 in combination with chemotherapy with ORR of nivolumab in combination with chemotherapy in randomized subjects with advanced or metastatic LAG-3 negative GC or GEJ	ORR in the LAG-3 negative group or overall is defined as above, as the number of subjects in each population with a BOR of CR or PR divided by the number of randomized

Table 3-1: Objectives and Endpoints

Objectives	Endpoints
adenocarcinoma, and overall (across LAG-3 negative and positive groups).	subjects in each Treatment Arm, for that population

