7.6.1 Deaths

Deaths will be summarized by treatment group. These analyses will be performed on the All Treated LAG-3 Positive Subjects, All Treated LAG-3 Negative Subjects, and All Treated Subjects.

- All deaths, reasons for death
- Deaths within 30 days of last dose received, reasons for death
- Deaths within 100 days of last dose received, reasons for death

A by-subject listing of deaths will be provided for the all enrolled subjects population.

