7.6.5 Adverse Events

Adverse events will be summarized by treatment group.

The following analyses will be conducted using the 30 days safety window only:

- Overall summary of any AEs by worst CTC grade (1, 2, 3, 4, 5, not reported, total) presented by SOC/PT. This analysis will be performed on the All Treated LAG-3 Positive Subjects, All Treated LAG-3 Negative Subjects, and All Treated Subjects, and All Treated Subjects by Chemotherapy
- Overall summary of any AEs presented by worst CTC grade (any grade, grade 3-4, grade 5) by SOC/PT. This table will be restricted to events with an incidence greater or equal to 5% in any treatment group.
- Overall summary of any non-serious AEs presented by SOC/PT. This table will be restricted to events with an incidence greater or equal to 5% in any treatment group
- Overall summary of any AEs that required immune modulating medication by worst CTC grade (any grade, grade 3-4, grade 5) presented by SOC/PT
- Overall summary of drug-related AEs by worst CTC grade (1, 2, 3, 4, 5, not reported, total) presented by SOC/PT. This analysis will be performed on the All Treated LAG-3 Positive Subjects, All Treated LAG-3 Negative Subjects, and All Treated Subjects.

The following analyses will be conducted using the 30 days safety window and repeated using the 100 days safety window:

- Overall summary of drug-related AEs by worst CTC grade (any grade, grade 3-4, grade 5) presented by SOC/PT

A by-subject AE listing will be provided. A by-subject listing of any AE requiring immune modulating medications will also be provided.

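### SAE tables stop 30 days after last dose although SAEs are collected to 100 days, so SAE incidence by arm is not reported for days 31 to 100

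*SAP*

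**What the plan says.** **Collection.** Protocol 9.2.1 requires SAEs from consent and "within 100 days of discontinuation of dosing". Protocol 9.2.2 asks for nonserious AEs during treatment and "for a minimum of 100 days following discontinuation of study treatment". Protocol 5.1.3 schedules an in-person visit at day 100.

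**Endpoint.** The secondary safety endpoint in SAP section 3 is "The incidence of AEs, SAEs, AE leading to discontinuation, deaths, and laboratory abnormalities in each arm", with no time window. Protocol 10.3.3 says that "All on-study AEs, treatment-related AEs, SAEs, and treatment-related SAEs will be tabulated using worst grade per NCI CTCAE v 5.0 criteria", again with no 30-day limit.

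**Analysis.** SAP 6.1 defines the post-treatment safety window as 30 or 100 days after last dose and leaves the choice to each analysis. For the SAE and drug-related SAE tables, 7.6.2 chooses 30 days: "All analyses will be conducted using the 30-day safety window". The serious select AE tables in 7.6.6.1 are also limited to 30 days.

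**Where the SAP goes to 100 days.** One drug-related AE table in 7.6.5 is "repeated using the 100 days safety window". The deaths section, 7.6.1, includes "Deaths within 100 days of last dose received, reasons for death". The IMAE tables (7.6.7) and OEOSI tables (7.6.8) also use 100 days.

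**The concern.** SAE incidence by arm is a named secondary endpoint, and its source data are gathered to day 100. The tables that report it stop at day 30, and the SAP gives no reason for treating SAEs differently from the categories it follows to day 100.

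Two features of this trial make the later period relevant. First, the randomized difference is an added checkpoint antibody. The protocol's contraception periods imply a half-life of about four weeks (worked out below), so the SAE tables close about one half-life after last dose. Second, the trial is open-label. The 100-day drug-related AE table depends on attribution by investigators who know the arm. An all-causality SAE table depends less on that judgement, and none is planned beyond day 30.

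At stake is how complete the descriptive safety comparison is. No hypothesis test or decision rule depends on it.

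**Working it through.** The plan states no figure to reproduce. The check compares windows, then traces where a late SAE would be counted.

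**1. Windows side by side**

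| Output | SAP section | Days after last dose | Identifies SAEs? |
|---|---|---|---|
| SAEs, all and drug-related | 7.6.2 | 30 | Yes |
| Serious select AEs, all and drug-related | 7.6.6.1 | 30 | Yes |
| All-causality AEs | 7.6.5 | 30 | No |
| Drug-related AEs by worst grade | 7.6.5 | 30 and 100 | No |
| IMAEs | 7.6.7 | 100 | No |
| OEOSI, all and drug-related | 7.6.8 | 100 | No |
| Deaths, with reasons | 7.6.1 | All, 30 and 100 | Deaths only |
| Exposure-adjusted AE counts | 7.6.9 | Not stated | No |

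**2. Where an SAE on days 31 to 100 is counted**

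- Drug-related: in the 100-day drug-related AE table, by grade. Grade does not stand in for seriousness.
- Immune-mediated: in the IMAE tables, without a seriousness split. Under 7.1.1.3, non-endocrine events qualify only if treated with immune-modulating medication.
- On the OEOSI term list: in the OEOSI tables, without a seriousness split.
- Fatal: in the 100-day deaths table. Death makes an event serious by definition, but the table counts deaths by reason and not SAEs by term.
- Non-fatal, judged unrelated, and neither IMAE nor OEOSI: in no table with a stated 100-day window. If 7.6.9 were run at 100 days it would include such an event, but not as serious.

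The SAP's late-emergent category (6.1) starts after day 100, so it does not cover the gap. The by-subject SAE listing in 7.6.2 has no stated window, but it gives no incidence by arm.

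**3. Size of the gap in days**

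(100 − 30) / 100 = 70% of the post-dose collection window. On the exposure convention in SAP 7.1.1 (31 and 101 days) it is (101 − 31) / 101 = 69.3%. This treats the protocol's discontinuation of dosing and the SAP's last dose as the same date.

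**4. Why 70% of days is not 70% of events**

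Suppose, as an assumption, that the post-dose SAE hazard halves every h days, with k = ln 2 / h. The share of day 1 to 100 events that fall after day 30 is (e^(−30k) − e^(−100k)) / (1 − e^(−100k)).

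| Assumed hazard | Share after day 30 |
|---|---|
| Constant | 70.0% |
| Halves every 60 days | 57.2% |
| Halves every 30 days | 44.5% |
| Halves every 15 days | 24.3% |

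The endpoint also counts SAEs during treatment. With T days on treatment, the omitted days are 70 / (T + 100) of SAE follow-up. For assumed durations of 3, 6 and 9 months (30.4375 days each), that is 36.6%, 24.8% and 18.7%.

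**5. Half-life implied by the contraception periods**

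Protocol 6.1 sets 24 weeks for women as 30 days plus about five half-lives: (168 − 30) / 5 = 27.6 days. It sets 33 weeks for men as 90 days plus about five half-lives: (231 − 90) / 5 = 28.2 days. Under simple exponential decay, 0.5^(30/27.6) = 47% of the antibody remains at day 30 and 0.5^(100/27.6) = 8% at day 100. The safety window runs from the last dose of any study treatment, so participants who stop immunotherapy before chemotherapy are covered for longer after their last antibody dose.

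**The case against.** The strongest reply is that this is a permitted choice. SAP 6.1 allows 30 or 100 days, the endpoint definition carries no window, and 30 days is also used for discontinuations, dose modifications, select AEs and laboratory tests. All of that stands. A reader might infer that 7.6.2 contradicts the endpoint or Protocol 10.3.3. The documents do not support that, because neither text fixes a window for SAEs.

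A second reply is that late toxicity is already tabulated by arm. This largely stands too. A reader might infer that the safety comparison cannot see late serious events, or that they appear only in listings. That is wrong: drug-related, immune-mediated, special-interest and fatal events all reach 100-day tables. The events that reach none are mainly non-fatal SAEs judged unrelated, which are arguably the least informative about immune toxicity. What the reply does not supply is the endpoint itself, SAE incidence by arm, over the collected period.

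Third, days 31 to 100 can include subsequent anticancer therapy, which mixes later treatment effects into an all-causality table. This also stands. It argues for showing both windows and against replacing the 30-day tables.

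Finally, table mock-ups are in a Data Presentation Plan and DMC outputs follow a charter, neither of which is available here. Parts of SAP 7.6 are also not shown. A 100-day SAE table could exist there, but the SAP text as it reads does not call for one.

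**Conclusion.** The point holds as a modest reporting gap. SAE and drug-related SAE incidence by arm is not summarized for 70 of the 100 post-dose days over which SAEs are collected, and no other table supplies it.

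A reader might take the 70% as the share of SAEs missed, or multiply an assumed SAE rate by the 125 or so participants per arm to get a count. The documents support neither. They give no SAE rates. Such a count would treat everyone randomized as treated, off treatment, alive and followed to day 100. It would also include participants already counted for an earlier SAE, although SAP 7.1.1 counts each subject once at subject level. The shares in the working show only how far the answer depends on the assumed hazard.

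The primary endpoint is unaffected. This is an inexpensive improvement and not an error that must be corrected before the analysis can stand.

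**What to change.** Keep the 30-day tables in SAP 7.6.2 and add a sentence that the SAE and drug-related SAE tables will be repeated with the 100-day window, as 7.6.5 already does for drug-related AEs. Preferably do the same for the serious and drug-related serious select AE tables in 7.6.6.1.

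Present the two windows together. Footnote the 100-day tables to say that days 31 to 100 may include subsequent anticancer therapy, and that participants still on treatment or not yet followed for 100 days at the data cutoff contribute less than the full window.

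The cost is two extra tables in 7.6.2 and a few more if the select AE tables are repeated. No new data collection is needed. The drawback is the possible overlap with subsequent therapy, which the 30-day tables shown alongside help the reader to judge.

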7.6.3 Adverse Events Leading to Discontinuation of Study Therapy

AEs leading to discontinuation will be summarized by treatment group. These analyses will be performed on the All Treated LAG-3 Positive Subjects, All Treated LAG-3 Negative Subjects, and All Treated Subjects.

- Overall summary of AEs leading to discontinuation by worst CTC grade (any grade, grade 3-4, grade 5) presented by SOC/PT
- Overall summary of drug-related AEs leading to discontinuation by worst CTC grade (any grade, grade 3-4, grade 5) presented by SOC/PT

The analyses will be conducted using the 30-day safety window.

A by-subject AEs leading to discontinuation listing will be provided.

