7.3.7 Criteria for BMS-986213 or Nivolumab Discontinuation

BMS-986213 or nivolumab should be permanently discontinued for the following:

- Any Grade 2 drug-related uveitis, eye pain, or blurred vision that does not respond to topical therapy and does not improve to Grade 1 severity within the re-treatment period OR requires systemic treatment.
- Any Grade 3 non-skin, drug-related AE lasting $>$ 7 days or recurs, with the following exceptions for laboratory abnormalities, diarrhea, colitis, neurologic toxicity, drug-related uveitis, pneumonitis, bronchospasm, hypersensitivity reactions, infusion reactions, and endocrinopathies:
 - Grade 3 drug-related diarrhea, colitis, neurologic toxicity, uveitis, pneumonitis, bronchospasm, hypersensitivity reaction, or infusion reaction of any duration requires discontinuation.
 - Grade 3 drug-related endocrinopathies adequately controlled with only physiologic hormone replacement do not require discontinuation. Adrenal insufficiency requires discontinuation, regardless of control with hormone replacement.

- Grade 3 drug-related laboratory abnormalities do not require treatment discontinuation except:
 - Grade 3 drug-related thrombocytopenia > 7 days or associated with bleeding requires discontinuation
 - Grade ≥ 3 drug-related AST, ALT, or total bilirubin requires discontinuation*
 - Concurrent AST or ALT > 3 × ULN AND total bilirubin > 2 × ULN requires discontinuation
- *In most cases of Grade 3 AST or ALT elevation, study drug(s) will be permanently discontinued. If the investigator determines a possible favorable benefit-risk ratio that warrants continuation of study drug(s), a discussion between the investigator and the BMS Medical Monitor/designee must occur.
- Grade 3 or higher myocarditis
 - Any Grade 4 drug-related AE or laboratory abnormality (including but not limited to creatinine, AST, ALT, or total bilirubin), except for the following events that do not require discontinuation:
 - Grade 4 neutropenia ≤ 7 days
 - Grade 4 lymphopenia or leukopenia or asymptomatic amylase or lipase
 - Isolated Grade 4 electrolyte imbalances/abnormalities that are not associated with clinical sequelae and are corrected with supplementation/appropriate management within 72 hours of their onset

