 - Grade 4 drug-related endocrinopathy AEs, such as, hyper- or hypothyroidism, or glucose intolerance, which resolve or are adequately controlled with physiologic hormone replacement (corticosteroids, thyroid hormones) or glucose-controlling agents, respectively, may not require discontinuation after discussion with and approval from the BMS Medical Monitor
 - Any event that leads to delay in dosing lasting > 8 weeks in the BMS-986213 or nivolumab PLUS FOLFOX treatment (or > 6 weeks in the BMS-986213 or nivolumab PLUS either XELOX or SOX treatment) from the previous dose requires discontinuation, with the following exceptions:
 - Dosing delays to allow for prolonged steroid tapers to manage drug-related AEs are allowed.
 - Dosing delays lasting > 8 weeks in the BMS-986213 or nivolumab PLUS FOLFOX treatment (or > 6 weeks in the BMS-986213 or nivolumab PLUS either XELOX or SOX treatment) from the previous dose that occur for non-drug-related reasons may be allowed if approved by the BMS medical monitor.
 - Any AE, laboratory abnormality, or intercurrent illness that, in the judgment of the Investigator, presents a substantial clinical risk to the participant with continued BMS-986213 or nivolumab dosing.

Prior to reinitiating treatment in a participant with a dosing delay lasting > 8 weeks in the BMS-986213 or nivolumab PLUS FOLFOX treatment (or > 6 weeks in the BMS-986213 or nivolumab PLUS either XELOX or SOX treatment) from the previous dose, the BMS Medical Monitor must be consulted. Tumor assessments should continue as per protocol even if dosing is delayed.

Periodic study visits to assess safety and laboratory studies should also continue every 6 weeks or more frequently if clinically indicated during such dosing delays.

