- ◆ For PD-L1, among the records prior to or on first dose date (and time if collected), identify first those with quantifiable test result. If there are no records with quantifiable test result, then select those with indeterminate result (“INDETERMINATE”). If there are no records with indeterminate test result, then select those with unavailable result (“NOT EVALUABLE”). If there are no records with unavailable test result, then select those with not reported or not available result (all other records). The latest record will be used as the baseline in the analyses. If there is more than one record for the latest date, then choose the one with the greatest specimen ID.

- Post baseline period:
 - On-treatment AEs will be defined as AEs with an onset date and time on or after the date and time of the first dose of study treatment (or with an onset date on or after the day of first dose of study treatment if time is not collected or is missing). For subjects who are off study treatment, AEs will be included if event occurred within a safety window of 30 days (or 100 days depending on the analysis) after the last dose of study treatment. No “subtracting rule” will be applied when an AE occurs both pre-treatment and post-treatment with the same preferred term and grade.
 - On-treatment evaluations (laboratory tests and vital signs) will be defined as evaluations taken after the day (and time, if collected and not missing) of first dose of study treatment. For subjects who are off study treatment, evaluations should be within a safety window of 30 days (or 100 days depending on the analysis) after the last dose of study treatment.
- Late-emergent drug-related AEs will be defined as drug-related AEs with an onset date greater than 100 days after the last dose of study treatment in subjects who are off study treatment.

- In addition, data collected within an extended follow-up window of 135 days based on specific EU country requests, will be presented in listings.

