7 STATISTICAL ANALYSES

7.1 General Methods

Unless otherwise noted, discrete variables will be tabulated by the frequency and proportion of subjects falling into each category, grouped by treatment. Percentages given in these tables will be rounded to the first decimal and, therefore, may not always sum to 100%. Percentages less than 0.1 will be indicated as '< 0.1'. Continuous variables will be summarized by treatment group using the mean, standard deviation, median, minimum, and maximum values.

Time-to-event variables (e.g., time-to resolution) will be analyzed using the Kaplan-Meier technique. When specified, the median will be reported along with 95% CI using Brookmeyer and Crowley method⁸ (using log-log transformation for constructing the confidence intervals⁹).

The conventions to be used for imputing missing and partial dates for analyses requiring dates are described in [Section 8](#).

7.1.1 Adverse Events, Serious Adverse Events, Multiple Events, Select Adverse Events, Other Events of Special Interest and Immune-Mediated Adverse Events

Drug-related AEs are those events with relationship to study drug "Related", as recorded on the CRF. If the relationship to study drug is missing, the AE will be considered as drug-related.

Serious adverse events consist of AEs deemed serious by the Investigator and flagged accordingly in the CRF and clinical database.

Adverse events leading to study drug discontinuation are AEs with action taken regarding study drug(s) = "Drug was discontinued".

Adverse events leading to dose delay are AEs with action taken regarding study drug(s) = "Drug was delayed".

Adverse events leading to dose reduction are AEs with action taken regarding study drug(s) = "Dose was reduced".

Adverse events will be coded using the Medical Dictionary for Regulatory Activities (MedDRA), and the most recent version of the dictionary at the time of the database lock will be used. Adverse event results will be graded for severity using the NCI Common Terminology Criteria for Adverse Events (CTCAE) and the version of the criteria specified in the protocol will be used.

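### The 30-day window on AEs leading to discontinuation is shorter than the permitted dose hold, so some treatment-ending events drop out of the SAP 7.6.3 and 7.6.6.1 summaries

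*SAP*

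**What the plan says.** The secondary safety endpoint in SAP Table 3-1 is "The incidence of AEs, SAEs, AE leading to discontinuation, deaths, and laboratory abnormalities in each arm". SAP 7.1.1 identifies an AE leading to discontinuation by the action taken on the CRF, with no time element. It also restricts AE summary tables to on-treatment events unless otherwise specified.

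For participants who have come off treatment, SAP 6.1 sets the upper limit of the on-treatment period as follows: "AEs will be included if event occurred within a safety window of 30 days (or 100 days depending on the analysis) after the last dose". SAP 7.6.3 chooses the shorter option: "The analyses will be conducted using the 30-day safety window". The select-AE tables in SAP 7.6.6.1, including those for discontinuation, also use 30 days only.

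Protocol 7.3.7 sets the interval after which immunotherapy must stop: "Any event that leads to delay in dosing lasting > 8 weeks in the BMS-986213 or nivolumab PLUS FOLFOX treatment", or more than 6 weeks with XELOX or SOX, counted from the previous dose. One exception has no stated upper limit: "Dosing delays to allow for prolonged steroid tapers to manage drug-related AEs are allowed". Protocol 7.3.3.1 lets a chemotherapy component be delayed by up to 6 weeks. Protocol 5.1.2 ends the Treatment Phase only when the participant is discontinued from study therapy.

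**The concern.** The endpoint concerns events that end treatment. The window that decides whether an event enters the summary starts at the last dose, not at the decision to stop, and it is shorter than the interval for which a participant may go undosed and still be in the Treatment Phase. The documents expect this situation: Follow-up Visit 1 moves to the discontinuation date when that date is more than 42 days after the last dose (Protocol 5.1.3, SAP 2.1).

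A participant who is stopped because of an event that began on, say, day 35 of a full hold is then off treatment, with an onset beyond day 30. Protocol 9.2.2 collects the event, since AE collection runs for at least 100 days after discontinuation, but the summary of a named secondary endpoint leaves it out. The participant could appear in the disposition table as a discontinuation for toxicity and be absent from the AE discontinuation table. Any such error goes one way: it lowers the stated incidence.

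**Working it through.** The plan gives no figure to reproduce. The check is day arithmetic.

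**Inputs**
- W = 30 days from last dose (SAP 6.1, 7.6.3).
- L = 6 × 7 = 42 days (XELOX/SOX) or 8 × 7 = 56 days (FOLFOX) from the previous immunotherapy dose (Protocol 7.3.7).
- d = days from the last immunotherapy dose to the last dose of any component, from the schedules in Protocol 7.1.2 to 7.1.4.
- I read last dose of study treatment as the last dose of any component. Protocol 7 lists the chemotherapy drugs as study treatment, and SAP 7.4.1 ends treatment duration at the last administered study therapy.

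**Formula:** uncovered days U = max(0, L − d − W).

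| Pattern | L | d | L − d | U |
|---|---|---|---|---|
| Q3W, immunotherapy alone | 42 | 0 | 42 | 12 (days 31–42) |
| Q3W, oral drug taken to Day 14, then all held | 42 | 13 | 29 | 0 |
| Q3W, chemotherapy continued at Day 22, oral to Day 35 | 42 | 34 | 8 | 0 |
| Q4W, immunotherapy alone | 56 | 0 | 56 | 26 (days 31–56) |
| FOLFOX on Days 1–2, then all held | 56 | 1 | 55 | 25 |
| FOLFOX alone on Days 15–16, then all held | 56 | 15 | 41 | 11 |
| FOLFOX continued to Days 43–44 | 56 | 43 | 13 | 0 |

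**Chemotherapy hold with no other drug given.** A delay of 42 days past schedule leaves between 21 − 13 + 42 = 50 days since last dose (oral drug) and 21 + 42 = 63 days (Q3W oxaliplatin). U is therefore 50 − 30 = 20 to 63 − 30 = 33.

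**With the 100-day window.** The longest interval above is 63 days, below 100, so U = 0 in every row. Only a hold beyond 100 days, such as a very long steroid taper, could leave a gap.

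**One event, two histories.** Take an onset 35 days after the last dose. With no further dose, 35 > 0 + 30, so it is excluded. With a further dose on day 42, 35 ≤ 42 + 30, so it is on-treatment.

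**A figure to reconcile.** SAP Table 7.4.2.1-1 gives 42 days as the maximum delay for both Q3W and Q4W immunotherapy, whereas Protocol 7.3.7 gives 8 weeks with FOLFOX. If 42 days were the interval from the previous dose, the Q4W gap on immunotherapy alone would be 42 − 30 = 12 rather than 26.

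**The case against.** The case against acting is that the gap is narrow and other outputs largely cover it. Most of this stands.

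- **Immune-mediated events are mostly caught.** SAP 7.6.7 tabulates immune-mediated AEs leading to discontinuation by arm at 100 days. A reader might infer that immune toxicity ending treatment goes uncounted. The documents do not support that: a Grade 3 hepatitis starting on day 35, treated with immune-modulating medication and without a clear alternate etiology, meets the definition in SAP 7.1.1.3 and appears there. Non-endocrine events not so treated, or with a clear alternate cause, do not.
- **Nothing need vanish from the report.** The by-subject listing in SAP 7.6.3 and the disposition table in SAP 7.3.1 state no window, and SAP 7.6.5 repeats the drug-related AE summary at 100 days. However, a listing gives no incidence by arm, disposition does not break events down by preferred term and grade, and 7.6.5 does not identify which events ended treatment.
- **A full hold is needed.** Protocol 7.3.1 and 7.3.5 have the other agents continue during a toxicity hold, which sets the gap to zero. Full holds remain possible, because Protocol 5.1.2 allows immunotherapy alone once chemotherapy is delayed or discontinued for toxicity.
- **Onset decides, not the stopping date.** An AE that caused the hold, or began in its first 30 days, is counted even if the decision to stop comes later.

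Three further inferences are tempting and go too far. First, that the same event enters the discontinuation table if dosing resumes. That is true of on-treatment status, but if the held drug itself restarts, the AE did not lead to its discontinuation and does not belong in 7.6.3. The contrast holds there only when one component is stopped and another is given again. Second, that 12/42 = 29% and 26/56 = 46% of events are lost. Those are shares of calendar days at the maximum interval. Third, that the relatlimab arm is favoured. Both arms contain nivolumab, and nothing in the documents shows more full holds with late-onset stopping events in either arm.

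**Conclusion.** The point holds in a limited form. The 30-day rule can leave treatment-ending AEs out of the incidence summaries in SAP 7.6.3 and the select-AE discontinuation tables in 7.6.6.1 when onset is more than 30 days after the last dose of any component. At the protocol's immunotherapy limits this exposes up to 12 days (Q3W) or 26 days (Q4W) on immunotherapy alone, more during prolonged tapers, and none when another component was given in the previous 30 days. The loss falls mainly on events that do not qualify as immune-mediated.

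This rests on two readings: that the window runs from the last dose of any component, and that the 7.6.3 listing, which states no window, is not itself cut at 30 days. The documents give no rates of full holds or late-onset stopping events, so the number affected cannot be estimated. The summaries are descriptive, so no test or decision rule changes. It is a cheap correction to a rule that can only undercount a named endpoint.

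**What to change.** In SAP 7.6.3 and the discontinuation rows of 7.6.6.1, include every AE with onset on or after first dose whose recorded action is drug discontinuation, with no upper limit relative to last dose. At minimum, repeat these summaries with the 100-day window that the SAP already uses in 7.6.5 and 7.6.7. That closes the gap at the 42- and 56-day limits but not for holds beyond 100 days. In either case, state which window the by-subject listing uses.

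The cost is one sentence and one program condition, or one repeated set of tables. No new data are needed, because AE action and onset are already collected. The stated discontinuation rate may rise slightly. Separately, reconcile the maximum delay in SAP Table 7.4.2.1-1 with Protocol 7.3.7.
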